## 2 Synopsis of clinical research

HumanITcare has implemented a cloud platform for telemonitoring of chronic patients through wearable medical devices and an alarm-based system that issues health alerts when a patient's biomedical

measurement is outside a predefined clinical range. The platform frees doctors and caregivers from reviewing each patient's data for anomalies, speeding up the decision-making process and reducing hospital visits. With the present study we aim to validate the effectiveness of the app for patients and digital platform for medical professionals by evaluating the increase in the quality of life of patients and measuring the reduction in the incidence of the main critical events of HF. Additionally, the study will validate the new API interoperability standards and platform architecture and evaluate the usability of the platform by delivering satisfaction questionnaires to patients and professionals at the end of the study.

This study is being carried out within the framework of a European project promoted by the European Innovation Council (EIC).

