### 6.2 Secondary objectives

- To evaluate the role of telemonitoring in identifying early signs of deterioration in patients with heart failure and triggering timely interventions to prevent exacerbations.
- Improve clinical outcomes for patients with heart failure, as well as reduce hospital readmissions.

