##### **Secondary endpoints**

- Quality of life evaluated through the "Minnesota Questionnaire for People with Heart Failure" (Change in the value of the questionnaire scale at 3 months)
- Patient-Reported Self-Care Behavior Scale Measures (EHFScB Scale) (Change in Questionnaire Scale Value at 3 Months)
- Patient adherence to treatment and medication intake (SMAQ Simplified Medication Adherence Questionnaire) (Change in the value of the questionnaire scale at 3 months)
- Death from cardiovascular (CV) causes (Total number of patients who died in 3 months)

- Mortality from any cause (Total number of patients who died in 3 months)
- Acute HF decompensation (first and recurrent) during the follow-up period (Number of total decompensations in 3 months).

An acute decompensation of HF is defined as a new episode of symptoms and signs that requires intravenous decongestive treatment or increased oral diuretics either on an outpatient basis (e.g., day or home hospitalization for HF) or at home, emergency department or requiring an unplanned hospital admission.

- Hospital readmission due to HF decompensation (Total number of hospitalizations in 3 months)
- Hospital readmission for CV causes (Total number of hospitalizations in 3 months)
- Visits to the emergency room due to HF decompensation (Total number of visits to the emergency room in 3 months)
- Visits to the emergency room for CV causes (Total number of visits to the emergency room in 3 months)
- Medical care costs (Sum of costs for medication consumption, hospitalization, emergency care and medical transportation in 3 months)

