#### 7.1.4 Sample calculation

The sample calculation has been made based on the fact that a change of 5 points on the scale of the Minnesota Questionnaire for People with Heart Failure (MLHF questionnaire) between the control group and the experimental group (telemonitored) is clinically significant. (Rector, n.d.). Assuming an alpha risk = 0.05 and a beta error of 20%, we need to recruit a total of 253 participants divided into a control group and an experimental group.

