## 8 Design and statistical analysis

### 8.1 Methodology and analysis

Specific subgroup analyzes will be performed based on the different baseline data and risk factors available for the project. We will also test interactions between each pair of subgroups and the main effect of treatment.

Independent t tests or Mann-Whitney U tests will be used to compare the questionnaire scores based on the distribution of the data, whether normally distributed or not, respectively.

The incidence of secondary endpoint events in the two study groups will be described using Kaplan-Meier survival curves, which will be compared using the log-rank test. The hazard ratio will also be obtained using Cox proportional hazards regression models comparing the TM and UC groups. The time of each event will be calculated from the day of registration. We will compare the number of readmissions and days of hospitalization between the two groups using the Wilcoxon rank sum test.

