### 16.2 Clinical evaluation plan

The analysis of the results and the final report will be part of the development of the Clinical Evaluation Plan (CEP) described in section A of annex XIV of regulation 2017/745, which is being developed as part of the technical documentation for obtaining the marking. CE of the product as a medical device.

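### Fewer critical HF events is a stated ground for validating effectiveness, but the seven secondary event endpoints have no deciding event, testing order, adjustment or supportive label

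*Combined protocol and SAP*

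**What the plan says.** Section 2 sets out how effectiveness will be validated: "by evaluating the increase in the quality of life of patients and measuring the reduction in the incidence of the main critical events of HF". It does not identify the main event. Section 6.2 places events among the secondary objectives: "Improve clinical outcomes for patients with heart failure, as well as reduce hospital readmissions". Section 6.3 also hypothesises better clinical outcomes.

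Under secondary endpoints, section 7.1.3 lists seven event endpoints without ranking: CV death, death from any cause, acute HF decompensation, readmission for HF, readmission for CV causes, emergency visits for HF and emergency visits for CV causes. The three questionnaire scores and medical costs appear in the same list. The non-fatal events are defined as totals, for example "Hospital readmission due to HF decompensation (Total number of hospitalizations in 3 months".

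Section 8.1 gives the event analysis: "The incidence of secondary endpoint events in the two study groups will be described using Kaplan-Meier survival curves, which will be compared using the log-rank" method, with hazard ratios from Cox models. It then adds: "We will compare the number of readmissions and days of hospitalization between the two groups using the Wilcoxon rank sum test". Length of stay is not an endpoint in 7.1.3. Section 8.1 names no test for costs.

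The only significance level is in section 7.1.4: "Assuming an alpha risk = 0.05 and a beta error of 20"%. It belongs to the MLHF sample size. For the secondary endpoints the plan gives no significance level, adjustment, testing order, key endpoint or supportive label. Section 16.2 states the use of the results: "The analysis of the results and the final report will be part of the development of the Clinical Evaluation Plan", as part of the technical documentation for CE marking.

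**The concern.** Secondary endpoints are often left unadjusted because they only support the primary. This plan does not say that, and its synopsis puts event reduction beside quality of life as a ground for validation. With seven unranked candidates, a reader of the final report could not tell a pre-specified event finding from the best of seven.

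There is also a choice within endpoints. Readmission is defined as a total, is covered by the time-to-event comparison, and is compared again as a count by Wilcoxon. HF and CV readmission can disagree, and so can time to first event and the number of events. No rule says which result stands.

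What is at stake is the reliability of any event claim carried into the clinical evaluation. The analysis of the primary endpoint is not affected.

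**Working it through.** **1. The plan's own figure.** No error rate is stated for the secondary family, so there is none to reproduce. The only related figure is the total of 253, from "a change of 5 points on the scale of the Minnesota Questionnaire for People with Heart Failure", alpha 0.05 and 80% power. The SD is not given. With n per group = 2(z₀.₉₇₅ + z₀.₈₀)² SD²/5² = 2 × (1.960 + 0.842)² × SD²/25, an SD of 14.0 gives 124 per group (248) and 14.2 gives 127 per group (254). So 253 implies an SD of about 14.2, two-sided and without dropout. The multiplicity question does not depend on this.

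**2. The family counted.** The seven event endpoints of 7.1.3, one log-rank test each. Costs are left out because 8.1 gives them no test. Each test is assumed two-sided at 0.05 (the plan does not state sidedness), which is 0.025 in the direction favouring telemonitoring (TM).

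**3. Independent tests (upper reference).**
- Either direction: 1 − 0.95⁷ = 0.302.
- Favouring TM: 1 − 0.975⁷ = 0.162.

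**4. Equal correlation ρ between the seven statistics.** Z_j = √ρ·U + √(1−ρ)·e_j, with U and e_j standard normal and 400,000 draws per ρ. Count the draws with any |Z_j| > 1.96, and those with any Z_j beyond 1.96 on the TM side.

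| ρ | Either direction | Favouring TM |
|---|---|---|
| 0 | 30.2% | 16.2% |
| 0.3 | 27.1% | 13.7% |
| 0.5 | 23.0% | 11.5% |
| 0.7 | 17.8% | 8.9% |
| 0.9 | 11.4% | 5.8% |
| one test | 5% | 2.5% |

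**5. Patient-level null simulation.** The seven endpoints overlap unevenly: HF readmissions are a subset of CV readmissions, and the same holds for emergency visits. Trials of 253 patients (127 and 126) over 90 days were simulated with no treatment effect, 6,000 per scenario. Assumptions, none from the documents: a mean of 0.5 HF decompensations per patient; an emergency visit after 60% of events; admission after 53% of events with an emergency visit and 12% of the others; death hazards over the period of 0.03 (CV) and 0.02 (non-CV); gamma frailty; and other CV events at a stated multiple of the HF rate.

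| Frailty variance | Other CV : HF | Any of 7, either direction | Any of 7, favouring TM |
|---|---|---|---|
| 0.5 | 0.3 | 20.3% | 10.6% |
| 0.5 | 0.6 | 21.1% | 11.3% |
| 1 | 0.3 | 20.4% | 10.6% |
| 1 | 1.0 | 22.5% | 11.8% |

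Each test alone rejected in about 4-6% of trials, so the inflation comes from the number of tests. The five non-fatal endpoints had test correlations of 0.49-0.88. The two death endpoints correlated at about 0.76 with each other and at most 0.09 with the rest. A second simulation with other assumed rates (3,000 trials in each of three scenarios) gave 21.0%, 19.9% and 20.5% in either direction.

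**6. The extra Wilcoxon tests.** Adding both Wilcoxon tests and a rank test on costs raised the either-direction figure to 23.1-24.9%. That includes a cost test the plan does not specify, so it is only an upper limit on what the two Wilcoxon tests add.

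**7. Inflation.** Favouring TM: 10.6/2.5 = 4.2 to 11.8/2.5 = 4.7 times the single-test rate. At ρ = 0.9 it is still 5.8/2.5 = 2.3 times.

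**The case against.** The best defence is that the plan already separates one principal endpoint from the secondary ones and puts readmissions under secondary objectives. Unadjusted secondary results read as supportive are ordinary practice. This stands in part. A reader might infer that one significant event is enough to declare success, or that events can carry the claim if the primary fails. No section says so, and 16.2 ties nothing to a secondary p-value. The error rates above are therefore conditional on such a result being used for the synopsis claim. The label does not settle the matter, however, because section 2 names event reduction as a ground for validation and nothing says it is only supportive. Section 2 also already cites fewer emergency returns and readmissions in the 32-patient pilot as evidence for the platform.

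Three stronger readings are tempting and should be resisted:
- The chance of a false effectiveness claim is 20-25%. That band counts results in which telemonitoring looks worse, which cannot support a claim of fewer events, and its top end needs costs as an eighth test.
- Costs are among the unadjusted tests. They are listed in 7.1.3, but 8.1 gives them no test.
- Section 6.2 selects HF readmission as the deciding event. It speaks of hospital readmissions in general, while 7.1.3 lists HF and CV readmission separately.

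It is also fair to object that the documents give no event rates or correlations, so no single percentage follows from them. A range is needed.

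**Conclusion.** The point holds. The plan makes event reduction a ground for validating effectiveness and compares seven unranked event endpoints, with two further Wilcoxon tests, without naming a deciding event, an order, an adjustment or a supportive status.

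If any nominal p<0.05 among the seven were used for that claim, the chance of a false result favouring telemonitoring would be about 11-12% against 2.5% for one test. It runs from about 6% at correlation 0.9 to 16% if the tests are independent. In either direction it is about 20-23% against 5%, with a range of 11-30%. The percentages depend on assumed rates and correlations and on two-sided testing at 0.05. The direction of the conclusion does not: even at correlation 0.9 the rate is more than twice nominal. The change should be made, but this is not a fault in the primary analysis.

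**What to change.** Amend sections 2, 7.1.3 and 8.1 before any data are seen, in one of two ways.

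**(a) One key event.** The sponsor names one key secondary event endpoint and one test for it. The choice is the sponsor's, since 6.2 does not separate HF from CV readmission. It is tested at two-sided 0.05 only after a positive primary result. That requires the plan to define a positive primary first: 7.1.3 describes a composite of three questionnaires without a rule for combining them, and 8.1 does not supply one. All other events, costs, hospital days and the second readmission test are reported as supportive estimates with 95% confidence intervals. The synopsis then rests validation on the primary and, where the sequence allows, on the key event.

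**(b) No ranked event.** All event and cost results are labelled supportive or exploratory and reported with 95% confidence intervals. The synopsis is reworded so that validation of effectiveness rests on the primary endpoint.

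Either option takes a few sentences, with no new data and no more patients; option (a) also needs the definition of a positive primary. The price is that a lone nominal p<0.05 on an unranked event can no longer be presented as proof of effectiveness.

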### Clinical data evaluation

Heart failure (HF) is a prevalent and fatal clinical syndrome that affects the quality of life of millions of people worldwide. Between 17% and 45% of patients with HF die within the first year and the rest die within 5 years (Tripoliti et al., 2017). Furthermore, these patients have a high risk of rehospitalization, their associated healthcare costs are enormous, and the longer the life expectancy, the higher the prevalence of the disease. (McDonagh et al., 2021). Symptoms of IC commonly include shortness of

breath, excessive tiredness, and swelling of the legs that may worsen with decompensation. (Schiff et al., 2003), so traveling to medical centers represents a disadvantage for these people. Remote monitoring technologies provide a feasible solution that allows for earlier identification of decompensation and better adherence to lifestyle changes and medication (Brahmbhatt & Cowie, 2019). Although telemonitoring using smartphones shows potential to reduce both the frequency and duration of hospitalizations for HF (Koulaouzidis et al., 2016) cannot be associated with reduced mortality from any cause (Koehler et al., 2011). Therefore, there is a need to search for more effective and precise methodologies. In recent years, the use of portable devices (wearables) that allow daily monitoring of the patient's physiological data combined with Artificial Intelligence (AI) has shown enormous potential to predict diseases related to the cardiovascular system, their adverse events and the patient's health status (Lee et al., 2022), including patients with HF (Guidi et al., 2015).

HumanITcare is a platform that allows this remote monitoring through the integration of different medical devices and self-reported data. The platform allows you to customize a monitoring plan so that healthcare professionals can adapt this tool to the needs of a specific patient group or at the individual patient level.

The HumanITcare platform has been used in different therapeutic areas to improve personalized patient monitoring. Some of the areas in which an improvement in patient monitoring and health status has been demonstrated would be cardiology (IC - (Sanchez et al., 2020); cardiac rehabilitation - (Calvo-López et al., 2023), palliative care (Castillo Padrós et al., 2022), respiratory diseases, or oncology, among others.

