#### 7.1.3 Variables

##### **Endpoint principal**

- Composite of quality of life, self-care and adherence to treatment by the patient (Change in the scale value of each questionnaire at 3 months)

The variables are quantified using validated scales. These measures are:

- Patient-Reported Self-Care Behavior Scale Measures (EHFScB Scale)
- Quality of life assessed through the "Minnesota Questionnaire for People with Heart Failure (MLHF questionnaire)"
- Patient adherence to treatment and medication intake (SMAQ Simplified Medication Adherence Questionnaire)

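### Early death is not accounted for in the rank comparison of readmissions and hospital days or in the 3-month questionnaire changes; if deaths differ between arms, both are modestly biased toward the arm with more deaths.

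*Combined protocol and SAP*

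**What the plan says.** The principal endpoint (7.1.3) is a composite of quality of life, self-care and treatment adherence, each measured as "Change in the scale value of each questionnaire at 3 months". The test is given in 8.1: "Independent t tests or Mann-Whitney U tests will be used to compare the questionnaire scores based on the distribution of the data".

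Readmission is a secondary endpoint defined as a raw total: "Hospital readmission due to HF decompensation (Total number of hospitalizations in 3 months"). For hospital use, 8.1 adds: "We will compare the number of readmissions and days of hospitalization between the two groups using the Wilcoxon rank sum test". Days of hospitalization appears only in that sentence; 7.1.3 does not list or define it.

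Death enters the plan in three places. Cardiovascular and all-cause death are separate secondary endpoints in 7.1.3. Secondary endpoint events are to be described by Kaplan-Meier curves and compared by log-rank test and Cox regression, timed from registration (8.1). Death is also listed among the withdrawal criteria (7.2.3).

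No section says how a patient who dies enters the questionnaire comparison or the Wilcoxon comparison. The only stated response to missing data is a follow-up call (7.4).

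**The concern.** A patient who dies on day 5 has 5 days in which to be admitted; a patient who lives has 90. Compared as raw totals, the early death without readmission gets the same value, zero, as a patient who stayed at home and well. A patient kept alive through an admission gets a worse value than either.

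The questionnaire change has a related problem. It does not exist for a patient who has died, and no follow-up call can supply it. The comparison is therefore among survivors, and if deaths differ by arm the survivors are no longer comparable groups.

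Both faults push the same way. If telemonitoring kept more of the sickest patients alive, both results would move against it; if it did the reverse, both would flatter it.

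**Working it through.** **Deaths to expect.** Section 4 (Clinical data evaluation) cites: "Between 17% and 45% of patients with HF die within the first year and the rest die within 5 years". With a constant hazard over the first year (an assumption), 3-month mortality is 1 − (1 − m)^0.25:

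- m = 0.17: 1 − 0.83^0.25 = 0.0455, and 253 × 0.0455 = 11.5
- m = 0.45: 1 − 0.55^0.25 = 0.1388, and 253 × 0.1388 = 35.1

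So about 12 to 35 of 253 patients would have no 3-month score.

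**The sample-size figure.** Section 7.1.4 gives a 5-point MLHF difference, alpha 0.05, 80% power and N = 253, but no SD, so 253 cannot be reproduced. Solving for the SD (two-sided, no dropout, 126.5 per arm): 5 / [√(2/126.5) × (1.960 + 0.842)] = 14.2. This SD is used below as an assumption. At equal mortality, losing 4.6% to 13.9% of patients lowers power from 80% to about 78% to 74%, without bias.

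**Direction and size of bias.** Simulation with 126 per arm, 1,500 runs per scenario and no true effect on score or admission rate. All of these inputs are assumed:

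- a shared frailty drives death, score and admissions; its correlation with the score is 0.3 to 0.7
- SD 14.2, with higher scores worse
- 0.5 admissions per 90 days, mean stay 8 days
- deaths spread evenly over the 90 days

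| | Deaths 4.6% v 4.6% | Deaths 13.9% v 4.6% |
|---|---|---|
| Survivors' MLHF change | about 0 | higher-mortality arm better by 0.3 to 0.7 points |
| Readmissions per patient | about 0 | better by about 0.03 |
| Hospital days per patient | about 0 | better by about 0.25 |
| Days lost to death or hospital | about 0 | worse by about 3.9 |

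A hand check of the last row: the extra deaths are 13.9% − 4.6% = 9.3% of patients, each losing 45 days on average, so 0.093 × 45 = 4.2 days. Less the apparent saving of 0.25 hospital days, that leaves about 3.9.

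The rate of significant results favouring the higher-mortality arm rises from about 2.5% to 3.7–5.1% for the score and 4.1–5.9% for hospital days. With 1,500 runs these rates carry a simulation error of about half a percentage point.

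**A smaller imbalance.** With deaths of 10% in usual care and 7% under telemonitoring and a true 5-point effect, the survivors' difference shrinks by about 0.2 points. Power is about 73%, and that includes the loss of the patients who died.

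**Cost of a worst-rank analysis.** With 10% deaths in each arm and a true 5-point effect, a Mann-Whitney test giving deaths the worst rank has about 60% power, against about 74% for the survivors-only test.

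**The case against.** The strongest reply is that the plan does not ignore death. Mortality is a secondary endpoint in its own right, and 8.1 plans Kaplan-Meier, log-rank and Cox analyses that include readmission. These use time at risk, so an early death is not credited with 90 event-free days. This stands as far as it goes: an imbalance in deaths would be visible. But those analyses do not correct the Wilcoxon comparison or the questionnaire comparison, and 8.1 does not say how death is treated when the event is a readmission.

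A second reply is that the bias is small and vanishes when deaths are equal. That is right, and it limits the weight of the point.

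Three stronger readings are tempting, and the documents do not support them.

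- A reader might infer that death distorts two main outcomes. Only the questionnaire composite is primary; readmissions are secondary, and hospital days is not a listed endpoint.
- A reader might infer that an early death earns the best rank outright. It ties at zero with every patient never readmitted, about 61% of patients at the assumed rate (e^−0.5 = 0.61), and a patient who dies during a readmission is counted as readmitted.
- A reader might infer a large loss of power by supposing that the extra survivors score 20 to 30 points worse than the rest. With deaths of 10% v 7% that gives a shift of 0.03 × 20/0.93 = 0.65 to 0.03 × 30/0.93 = 0.97 points. But such a gap is 1.4 to 2.1 SDs at SD 14.2, and nothing in the documents supports it.

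Nor do the documents predict a mortality benefit. No objective or hypothesis in section 6 names mortality, and section 4 says smartphone telemonitoring has not been associated with lower all-cause mortality.

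**Conclusion.** The point holds as a modest, conditional bias that is cheap to remove. The hospital-use comparison takes no account of time alive, and the questionnaire changes exist for survivors only. At 13.9% against 4.6% deaths, the arm with more deaths appears slightly better on both while doing clearly worse on time alive and out of hospital.

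The number of deaths rests on a constant hazard applied to the cited one-year range. The size of the bias rests on the assumed frailty link, SD, admission rate and length of stay; the documents give none of these, and no mortality by arm. The direction follows from the definitions, provided that sicker patients are the ones who die.

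Death is part of a wider gap. There is no statistical method for missing scores, and disease progression is itself a withdrawal criterion (7.2.3), so sick survivors could drop out of the comparison in the same way.

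**What to change.** 1. In 8.1, replace days of hospitalization with days lost to death or hospitalization within 90 days of registration, counting every day after death as lost, and compare it by the Wilcoxon test already planned. Define it in 7.1.3 as a secondary endpoint. Report raw hospital days and readmission counts descriptively, beside deaths by arm. The definition should also say how patients withdrawn alive are handled, and whether the rest of the index stay counts for those enrolled before discharge.

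2. Keep the survivors' comparison of questionnaire scores as planned. Add a pre-specified sensitivity analysis for MLHF, EHFScB and SMAQ, and for the composite once its scoring is fixed: a Mann-Whitney test giving patients who die before Day 90 the worst rank.

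**Cost.** Dates of death and readmission are already recorded in both arms (Table 1), and 7.4 provides for event dates and durations. The worst-rank result is not in scale points and loses power when mortality is equal, so it should only supplement the survivors' comparison. Because protocol and analysis plan are one document, the change may need the modification procedure in section 10.
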